NON-INTERVENTIONAL STUDY (NIS) PROTOCOL

PASS information

ENCEPP/SDPP/13422

Title	Healthcare Professional and Patient Surveys to Assess the Effectiveness of Additional Risk Minimisation Measures for Concentrated Insulin Lispro (Humalog 200 units/ml KwikPen; Liprolog 200 units/ml KwikPen)
Protocol version identifier	Version 1.0
Date of last version of protocol	30 November 2015
EU Post Authorisation Study (PAS) register number	
Active substance	Drugs Used in Diabetes, Insulin Lispro ATC code: A10AB04
Medicinal product	Humalog 200 units/ml KwikPen Liprolog 200 units/ml KwikPen (in Germany only) (For purposes of this protocol, the term Humalog 200 units/ml KwikPen will refer to both trade names Humalog and Liprolog)
Product reference	EU/1/96/007/039-042 EU/1/01/195/028-29
Procedure number	EMEA/H/C/000088/MEA/025
Marketing Authorisation Holder (MAH)	Eli Lilly Nederland B.V.
Joint PASS	No

**Non-Interventional Study Protocol
for Humalog 200 units/ml KwikPen
Version 1.0**

Research question and objectives	This study aims to evaluate the impact of the additional risk minimisation measures on healthcare professional and patient understanding and behaviour regarding the risk of hypoglycaemia and/or hyperglycaemia due to medication errors associated with administration of Humalog 200 units/ml KwikPen.
Country(-ies) of study	Germany, United Kingdom (UK, if product uptake does not allow for participation, another comparable EU country will be selected), and a 3 rd country to be determined based on launch and product uptake.
Author	[name], Pharmacoepidemiologist Eli Lilly and Company

Marketing Authorisation Holder(s)

Marketing Authorisation Holder(s)	Eli Lilly Nederland B.V. [name] The Netherlands
MAH contact person	[name], Pharmacoepidemiologist Eli Lilly and Company

1. Table of Contents

Section	Page
1. Table of Contents.....	4
2. List of abbreviations.....	8
3. Responsible parties	10
4. Abstract	11
4.1. Rationale and Background.....	11
4.2. Research Questions and Objectives	12
4.3. Study Design.....	12
4.4. Populations	13
4.5. Study Endpoints	13
4.6. Variables.....	14
4.7. Data Sources	14
4.8. Study Size	14
4.9. Data Analysis.....	14
4.10. Milestones.....	14
5. Amendments and updates.....	16
6. Milestones.....	17
7. Rationale and background	18
8. Research question and objectives	20
9. Research methods	22
9.1. Study design.....	22
9.2. Setting.....	23
9.2.1. Inclusion criteria	24
9.2.2. Exclusion criteria	25
9.3. Variables.....	25

10.2. Respondent withdrawal33

10.3. Independent Ethics Committee (IEC).....33

10.4. Ethical Conduct of the Study.....33

11. Management and reporting of adverse events/adverse reactions35

12. Plans for disseminating and communicating study results.....36

13. References37

List of Tables

Table		Page
Table 1.	Sample size calculations	29

List of Annexes

Annex		Page
Annex 1.	List of Standalone Documents	39
Annex 2.	ENCePP Checklist for study protocols.....	68
Annex 3.	Additional Information	77

2. List of abbreviations

Abbreviation	Definition
AE	Adverse Event
aRMM	Additional Risk Minimisation Measures
BfArM	Federal Institute for Drugs and Medicinal Devices (Germany)
CIOMS	Council for International Organisations of Medical Sciences
CIs	Confidence Intervals
DHPC	Direct Healthcare Professional Communication
EC	Ethics Committee
EDC	Electronic Data Capture
EMA	European Medicines Agency
ENCePP	European Network of Centres for Pharmacoepidemiology and Pharmacovigilance
EU	European Union
FDA	(US) Food and Drug Administration
GEP	Good Epidemiological Practice
GPP	Good Pharmacoepidemiology Practices
GVP	Guideline on Good Pharmacovigilance Practices
HCPs	Healthcare Professionals
ID	Identification
IEA	International Epidemiological Association
IEC	Independent Ethics Committee
ISPOR	International Society for Pharmacoeconomics and Outcomes Research
ISPE	International Society for Pharmacoepidemiology

**Non-Interventional Study Protocol
for Humalog 200 units/ml KwikPen
Version 1.0**

Abbreviation	Definition
IT	Information Technology
Lilly	Eli Lilly Nederland B.V.
MHRA	Medicines and Healthcare products Regulatory Agency
NIS	Non-interventional Study
PASS	Post-Authorisation Safety Studies
PRAC	Pharmacovigilance Risk Assessment Committee
RM	Risk Minimisation
RMM	Risk Minimisation Measures
SAP	Statistical Analysis Plan
SDLC	System Development Life Cycle
SOPs	Standard Operating Procedures
T2DM	Type 2 Diabetes Mellitus
UAT	User Acceptance Testing
UBC	United BioSource Corporation
UK	United Kingdom
US	United States

3. Responsible parties

Principal Investigator(s) of the Protocol

Name, degree(s)	Title	Affiliation	Address
[name]	Pharmacoepidemiologist	Eli Lilly and Company	

4. Abstract

Protocol Version 1.0—Healthcare Professional (HCP) and Patient Surveys to Assess the Effectiveness of Risk Minimisation Measures for Concentrated Insulin Lispro (Humalog 200 units/ml KwikPen; Liprolog 200 units/ml KwikPen)

4.1. Rationale and Background

Diabetes, especially type 2 diabetes mellitus (T2DM), is increasing in global prevalence and associated economic and humanistic burdens. Despite tangible improvement in disease management, poor glycaemic control remains a problem in individuals with diabetes (Inzucchi et al, 2012). Diabetes management guidelines recommend early initiation of insulin therapy in individuals with poor T2DM control or those with poor response to other anti-diabetes medications (Petznick A, 2011; ADA, 2014). In addition, insulin resistance and progressive loss of pancreatic beta-cell function are prodromal features of T2DM, which partially contribute to the need for high-dose insulin therapy—worldwide, about 30% of patients using basal insulin require more than 60 units daily (Gough et al, 2013), and approximately half of patients with T2DM will eventually require insulin to manage their diabetes (Jabbour, 2008).

Insulin formulations are listed among the high-alert medications that have potential to cause significant patient harm due to medication errors—errors that occur across the continuum of medication-use processes; however, insulin prescribing and administration related medication errors are most common (Cobaugh et al, 2013). Medication errors involving insulin may include inadvertent interchange between insulin strengths or formulations, incorrect dosage, or incorrect use of pen-injector devices. These errors may result in hyper/hypoglycaemia.

Humalog 200 units/ml KwikPen is a prefilled and disposable pen-injector device (pen) that delivers subcutaneous injection of 200 units/ml insulin lispro for the maintenance of normal glucose homeostasis in adults with diabetes mellitus. Despite warning messages on the pen and in the instructions for use, results from Human Factors studies performed in the United States (US) showed that a small percentage of patients may choose to withdraw insulin from the pen cartridge with a syringe if faced with device malfunction. Anecdotal information also indicates that patients in the European Union (EU) may transfer insulin lispro from the pen cartridge into an insulin pump. Because of these data and to further optimise the benefit-risk balance of the formulation, additional risk minimisation measures beyond routine risk minimisation measures are being conducted.

The additional risk minimisation measures will include a Direct Healthcare Professional Communication (DHPC) that will be distributed to all healthcare professionals (HCPs) who are expected to be involved in the treatment and management of patients with diabetes; physicians, nurses, and where applicable, pharmacists who are expected to dispense medications for diabetes management. A patient communication document will be distributed to prescribing HCPs targeted for the DHPC. The DHPC will ask HCPs to provide the patient communication to patients receiving their initial prescription of Humalog 200 units/ml KwikPen. Where approved,

a web address link to the patient communication may be provided in the DHPC to allow either printing of the communication during the patient visit or provision of the link to the patient to enable the patient to directly access the communication.

4.2. Research Questions and Objectives

This primary study objective is to evaluate the effectiveness of the additional risk minimisation activities on HCP and patient understanding regarding the risk of hypoglycaemia and/or hyperglycaemia due to medication errors/ misuse associated with administration of Humalog 200 units/ml KwikPen

The secondary objective is to evaluate behaviour of HCPs and patients regarding the risk of hypoglycaemia and/or hyperglycaemia due to medication errors associated with administration of Humalog 200 units/ml KwikPen as communicated through the risk minimisation measures.

Specifically, this protocol refers to the surveys that are designed to assess the effectiveness of communications to HCPs and patients by assessing their understanding of the risks and safe use of Humalog 200 units/ml KwikPen which were communicated through the risk minimisation measures.

4.3. Study Design

This study will be multi-national, observational, and cross-sectional in design. Separate surveys have been developed for HCPs and patients to enable the study objectives to be met. User Testing has been performed on each survey with samples of HCPs and patients and the feedback and recommended modifications have been incorporated into the surveys.

HCPs:

Surveys targeting eligible HCPs will be administered via the Internet, which will allow respondents to participate at a time and location that is convenient for them and by telephone to allow participation by respondents who may not have Internet access. Each invitation will include information on how to access the online survey and provide the toll-free number for accessing the telephone survey. Respondent-identifying information will be collected for the purposes of providing payment as allowed by local laws.

Patients:

Surveys targeting eligible patients will be administered via the Internet, which will allow respondents to participate at a time and location that is convenient for them and by telephone, which will allow participation of respondents who do not have Internet access or who are not computer literate. Each invitation will include information on how to access the online survey and will provide the toll-free number for accessing the telephone survey. Alternate modalities such as paper versions of the survey with a postage paid envelope for returning the completed survey, will be provided if the Internet and telephone modalities are found to be barriers to participation, or if disability proves to be a limiting factor (for example, a deaf patient who is not

computer literate). Respondent-identifying information will be collected for the purposes of providing payment as allowed by local laws.

4.4. Populations

The survey will be administered to HCPs and patients in the United Kingdom (UK, if product uptake does not allow for participation, another comparable EU country will be selected), Germany, and one additional EU country, to be determined based on product launch and market uptake. The timing of survey implementation will vary according to the individual country launch plans and the extent of Humalog 200 units/ml KwikPen uptake after launch. Screening questions will be used to determine respondent eligibility.

HCPs:

HCPs involved in the treatment and management of patients with diabetes who are aware of the insulin product Humalog 200 units/ml KwikPen will be eligible. The respondent population will include a mix of prescribers who have and have not prescribed Humalog 200 units/ml. Those employed in research full-time or hospital administration and those who have ever worked for or have immediate family members who have ever worked for Eli Lilly and Company (Lilly), United BioSource (UBC), or any national regulatory agency, such as but not limited to European Medicines Agency (EMA), Medicines and Healthcare products Regulatory Agency (MHRA) and Federal Institute for Drugs and Medicinal Devices (BfArM) will be excluded.

Patients:

Patients who are 18 years or older, have diabetes and have been prescribed Humalog 200 units/ml KwikPen will be eligible. Those who have ever worked for or have immediate family members who have ever worked for Lilly, UBC, or any national regulatory agency, such as but not limited to EMA, MHRA, and BfArM will be excluded.

4.5. Study Endpoints

The additional risk minimisation measures will be considered effective if the majority of respondents demonstrate they are aware of the key risks communicated.

HCPs:

- Demonstrating that they understand the key safety messages communicated in the DHPC
- Reporting that they provide patients with a copy of or means to access the Humalog 200 units/ml KwikPen patient communication at the time of initial prescription
- Reporting they discuss the key safety messages in the patient communication to their patients who are receiving their first prescription of Humalog 200 units/ml KwikPen.

Patients:

- Demonstrating that they understand the key safety messages communicated about Humalog 200 units/ml KwikPen

- Reporting that they were provided with a copy of or means to access the Humalog 200 units/ml KwikPen patient communication from their HCP at the time of initial prescription
- Reporting that they take into account the key messages during administration of Humalog 200 units/ml KwikPen.

All statistical analyses will be descriptive, that is, no formal hypothesis will be tested.

4.6. Variables

The survey will collect each eligible participant's understanding of the key safety messages in the risk minimisation communication and potential behaviour regarding their treatment with Humalog 200 units/ml KwikPen. The survey will also collect demographic characteristics for all respondents. For HCPs, demographics include age, sex, geographical location, specialty and practice information, and experience with Humalog 200 units/ml KwikPen. For patients, demographics include age, sex, geographical location, length of time with diabetes and length of time of using any insulin therapy and Humalog 200 units/ml KwikPen.

4.7. Data Sources

Structured, self-administered surveys comprised of closed-ended questions or statements with multiple response choices (that is, questions or statements asking the respondent to choose from a defined list of responses) will be used to collect the survey data from random samples of HCPs (Appendix 1.1) and patients (Appendix 1.3).

4.8. Study Size

The target sample sizes for the HCP and patient populations are 280 completed surveys each. With a sample size of 280 completed surveys, the true value of the correctly answered questions lies within the 95% confidence interval (CI) of the observed response. This yields the largest sample size required to achieve response rates with CIs of a half-width of 5%.

The HCP and patient samples will be divided according to the distribution of eligible participants in each country. The electronic data capture (EDC) system will be programmed to ensure desired distribution by requiring a minimum number of eligible participants from each country. Both unweighted and weighted results will be presented in the final report.

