Eligible HCPs will receive an invitation letter via email if an email address is available, or a letter in the postal mail inviting them to participate in the survey. The invitation letter (Appendix I.2) will include: an overview of the rationale for the survey, information on how to access the survey online and by telephone, and a unique User Identification (ID) to ensure that the invitation is used only once.

HCPs in the applicable countries who are involved in the treatment and management of patients with diabetes will be invited to participate in the survey. The respondent population will include a mix of prescribers who have and have not prescribed Humalog 200 units/ml. The response rate will be monitored throughout the data collection period. Reminder notices will be sent via email and postal mail, and telephone calls will be made periodically to HCPs who have been invited

but not yet participated. The HCPs that complete the survey will be reimbursed for their time spent participating as governed by local laws and country regulations.

Patients:

Surveys targeting eligible patients will be administered via the Internet, which will allow respondents to participate at a time and location that is convenient for them, and by telephone, to allow participation of respondents who do not have Internet access or are not computer literate. Both modalities will offer the same survey.

Patients will be recruited via study packets that will be provided to HCPs due to privacy concerns in the EU. All HCPs who receive an invitation to participate in the HCP survey will also receive a study packet of patient invitations in the postal mail and a letter asking them to invite eligible patients to participate in the survey. The packet will contain 10 invitation letters to be distributed. The patient invitation letter (Appendix I.4) will include an overview of the rationale for the survey, information on how to access the survey online, the toll-free number for accessing the telephone survey, and a unique User ID to ensure that the invitation is used only once. The HCPs will not be asked to select specific patients based on eligibility criteria. HCPs will forward the patient invitations to their patients for whom they have prescribed Humalog 200 units/ml. In the event an HCP has prescribed Humalog 200 units/ml to more than 10 patients, the HCP will arbitrarily select 10 patients regardless of any additional eligibility criteria.

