9.5. Study size

The target sample sizes for the HCP and patient populations are 280 completed surveys for each population. This sample size was determined based on the width of confidence intervals it will provide. [Table 1](#) shows 2-sided 95% confidence intervals based on the normal approximation to the binomial distribution ([Equation 1](#)) for a single sample of size of 280.

The samples will be divided by countries according to the distribution of eligible participants in each country. The EDC system will be programmed with country-specific limits to ensure desired distribution. Both unweighted and weighted results will be presented in the final report.

Equation 1.

$$95\%CI = Response\ Rate \pm 1.96 \left\{ \sqrt{\left[\frac{Response\ Rate(1-Response\ Rate)}{Sample\ Size} \right]} \right\}$$

Table 1. Sample size calculations

Sample Size	Observed Response Rate* (e.g. Knowledge)	2-Sided 95% Confidence Interval		
		Half-width	Lower Limit	Upper Limit
280	50%	5.9%	44.1%	55.9%
	60%	5.7%	54.3%	65.7%
	70%	5.4%	64.6%	75.4%
	80%	4.7%	75.3%	84.7%
	90%	3.5%	86.5%	93.5%

*Percentage of responders who correctly answered a question.

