Thank you in advance for your participation. Please note the application will time out after 30 minutes of inactivity.

If you are ready to begin the survey at this time, please click continue. If not, click Return Later.

Please note: Do not use the browser's back button during this survey.

[END WELCOME PAGE]

16. Are you familiar with the patient communication: *IMPORTANT SAFETY INFORMATION FOR Humalog 200 units/ml KwikPen (insulin lispro)* provided by Eli Lilly and Company?

- Yes
- No **[GO TO Q18]**
- I don't know **[GO TO Q18]**

17. Did you read the patient communication: *IMPORTANT SAFETY INFORMATION FOR Humalog 200 units/ml KwikPen (insulin lispro)* provided by Eli Lilly and Company?

- Yes
- No
- I don't know

18. **[DISPLAY ONLY IN [ENTER COUNTRY THAT HAS WEBSITE]** Are you aware of the website [ENTER WEBSITE], at which patients can access the patient communication: *IMPORTANT SAFETY INFORMATION FOR Humalog 200 units/ml KwikPen (insulin lispro)*?

- Yes
- No
- I don't know

[DO NOT DISPLAY IF 0 IS SELECTED IN Q8]

[DISPLAY ONLY IN [ENTER COUNTRY THAT DOES NOT HAVE WEBSITE]
Do you or another healthcare professional at your practice provide the patient communication: *IMPORTANT SAFETY INFORMATION FOR Humalog 200 units/ml KwikPen (insulin lispro)*, to patients receiving their first prescription of Humalog 200 units/ml KwikPen?

19.

Do you or someone at your practice provide the patient communication: *IMPORTANT SAFETY INFORMATION FOR Humalog 200 units/ml KwikPen (insulin lispro)* or the website at which the communication can be accessed, to patients receiving their first prescription?

- Yes

- No
- I don't know

[DO NOT DISPLAY IF 0 IS SELECTED IN Q8]

20. Do you or another healthcare professional at your practice discuss the patient communication: *IMPORTANT SAFETY INFORMATION FOR Humalog 200 units/ml KwikPen (insulin lispro)* with patients at the time of initial prescription of Humalog 200 units/ml KwikPen?

- Yes
- No
- I don't know

[PHONE ONLY: BEGIN SAFETY EVENT]

(INTERVIEWER: Please record if respondent spontaneously reported a safety event or product complaint during the course of this interview.)

- Yes
- No **[GO TO END SAFETY EVENT SECTION]**

Enter Safety Event or Product Complaint Verbatim

[MULTILINE INPUT]

(INTERVIEWER: Refer to Project Specific Procedure for next steps.)

[END SAFETY EVENT]

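### Abstract section 4.8 says 280 surveys are enough for a 5% half-width, but Table 1 in section 9.5 shows up to 5.9% at that size

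*Protocol*

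**What the plan says.** Section 4.8 of the protocol gives the target: "The target sample sizes for the HCP and patient populations are 280 completed surveys each". It then says that, with this number, the true value lies inside the 95% confidence interval of the observed response, and continues: "This yields the largest sample size required to achieve response rates with CIs of a half-width of 5" (per cent).

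Section 9.5 repeats the 280 but names no 5% target. Its rationale is: "This sample size was determined based on the width of confidence intervals it will provide". The method is "2-sided 95% confidence intervals based on the normal approximation to the binomial distribution" (Equation 1). The first two rows of Table 1 read "50% 5.9% 44.1% 55.9" and "60% 5.7% 54.3% 65.7" (rate, half-width, lower limit, upper limit). The remaining half-widths are 5.4% at 70%, 4.7% at 80% and 3.5% at 90%.

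On denominators, two questions in Appendix I.1 carry the instruction "DO NOT DISPLAY IF 0 IS SELECTED IN Q8": Q19 (providing the patient communication) and Q20 (discussing it). Section 9.2 says of the HCP sample: "The respondent population will include a mix of prescribers who have and have not prescribed Humalog 200 units/ml".

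**The concern.** The largest sample size required for a given half-width is the one at a true rate of 50%, where binomial variance is greatest. The abstract therefore reads as a promise that no question will have a half-width above 5%. Three of the five rows in the protocol's own table break that promise.

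Interval width is the only justification offered for the sample size, so a wrong figure in the abstract misstates that justification to anyone who reads only the abstract. The gap is widest near 50%, which is also where the effectiveness criterion of sections 4.5 and 9.1 (a majority of respondents) lies.

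The adjoining sentence is also wrong as written. A 95% interval covers the true value in 95% of repeated samples under its assumptions, and no sample size guarantees coverage in the one sample drawn.

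A smaller matter is that Table 1 is computed for a single sample of 280, while Q19 and Q20 are not shown to every HCP.

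**Working it through.** **Inputs.** n = 280 (sections 4.8 and 9.5); two-sided 95% normal-approximation interval with multiplier 1.96 (Equation 1); claimed half-width 5% (section 4.8).

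**Step 1: reproduce Table 1.** Half-width = 1.96 × √[p(1 − p)/280]. At p = 50% this is 1.96 × √(0.25/280) = 5.86%.

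**Step 2: sample size for a 5% half-width.** n = 1.96² × p(1 − p)/0.05². At p = 50% this is 3.8416 × 0.25/0.0025 = 384.16, rounded up to 385.

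| Rate correct | Half-width at n = 280 | Table 1 | n needed for 5% |
|---|---|---|---|
| 50% | 5.86% | 5.9% | 385 |
| 60% | 5.74% | 5.7% | 369 |
| 70% | 5.37% | 5.4% | 323 |
| 80% | 4.69% | 4.7% | 246 |
| 90% | 3.51% | 3.5% | 139 |

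Every row of Table 1 reproduces. The abstract's statement does not: the largest requirement is 385, which is 105 more than 280.

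**Step 3: where 280 does give 5%.** Set p(1 − p) = 280 × (0.05/1.96)² = 0.1822. Then p = 0.5 ± √(0.25 − 0.1822), which is 76.0% or 24.0%. The half-width is 5% or less only at or above about 76%, or at or below about 24%.

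**Step 4: could another reading rescue the claim?** At n = 280 and p = 50%:
- Wilson gives 5.8%; Clopper-Pearson and the continuity-corrected interval each give 6.0%.
- A 90% interval gives 4.9%, but both sections specify 95%.
- A finite-population correction gives 280 only for a population of about 1,030, which the protocol does not mention.

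**Step 5: Q19 and Q20.** Q8 is not in the text at hand. Section 9.4 lists the number of treated patients managed in the preceding 12 months as a survey variable, so Q8 is apparently that count. The protocol gives no share of HCPs who would select 0. The shares below are assumptions, to show the range only:

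| Assumed share shown Q19/Q20 | n | Half-width at 50% | Half-width at 80% |
|---|---|---|---|
| 90% | 252 | 6.2% | 4.9% |
| 75% | 210 | 6.8% | 5.4% |
| 50% | 140 | 8.3% | 6.6% |
| 25% | 70 | 11.7% | 9.4% |

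**The case against.** The best defence is that the operative section is already right. Section 9.5 sets no 5% target and displays the true widths, so a reader of the sample-size section is not misled. The worst-case gap is 0.9 points (44.1% to 55.9% instead of 45% to 55%). All analyses are descriptive, and no rule requires a confidence limit to clear 50% or a half-width to be met. This defence stands as to severity. It does not make the abstract sentence true.

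A reader might infer that the study is undersized and must go to 385 per population. The documents do not support that: section 9.5 justifies 280 by the widths it gives, and those widths are correctly stated.

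A reader might also infer that the HCP behaviour endpoints fall well short of Table 1. That is not established either:
- The content of Q8 is inferred.
- Not having prescribed is not the same as managing no treated patients. A nurse, for example, may manage such patients without prescribing.
- No share is given, and under a high share the loss is small.
- The footnote to Table 1 defines its rate as the share answering a question correctly, whereas Q19 and Q20 are practice reports.
- Section 9.9.1 openly says that skip logic may withhold questions.

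What remains is that these two items will probably have a denominator below 280, of unknown size.

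**Conclusion.** The contradiction between section 4.8 and section 9.5 is real and rests on the protocol's own formula alone. At 280 the half-width is at most 5.9%. It exceeds 5% for observed rates between about 24% and 76%, and a worst-case 5% would need 385. Section 9.5 and Table 1 contain no error.

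Severity is minor to moderate: a stated precision figure is wrong, but the sample size, the analysis and the effectiveness criterion are unaffected by putting it right.

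The note on Q19 and Q20 is secondary. It depends on Q8 being the count of treated patients managed, and the size of any loss cannot be fixed from the document.

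**What to change.** 1. In section 4.8, replace the half-width sentence with: *280 completed surveys give a 95% CI half-width of at most 5.9% (worst case 50%), and 5% or less only when the observed rate is at least about 76% or at most about 24%.*
2. In the same section, delete the sentence that places the true value inside the interval, or reword it in terms of coverage over repeated samples.
3. In section 9.5, leave the equation and table as they are and add one sentence: Table 1 applies only to questions shown to all 280 respondents, and Q19 and Q20 of the HCP survey may have a smaller denominator.

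The cost is three small edits to wording. No extra respondents, no new analysis and no change to Table 1 are needed. The abstract's stated precision becomes slightly less favourable, and correct.
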